- For explorative analysis research procedure, tumor tissue (lymph node core biopsy for NHL patients or tumor biopsy for patients with advanced solid malignancy) will be obtained pre- treatment (Day -30 to Day 7), C1D26 (± 7 days), and at C6D1 (± 7 days) and/or at the time of progression. Each biopsy will be divided into 3 portions, resulting in two fresh biopsies and one formalin fixed biopsy. Dose Escalation Phase: Patients will be enrolled according to their NAPRT1 status at a ratio of 2:1 (NAPRT1 negative:NAPRT1 positive). The NAPRT1 status must be determined prior to enrollment. NAPRT1 and IDH1 tumor status must be determined for all patients prior to enrollment in the KPT-9274 \pm niacin ER expansion cohort. Prescreening to determine NAPRT1 and IDH1 tumor status will be performed on archival biopsy material obtained ≤ 6 months prior to screening, followed by confirmation of NAPRT1 and IDH1 tumor status during screening period. *For the biopsies on C1D26 and C6D1 only, patients will be allowed to continue treatment if: 1) a patient refuses the biopsy, 2) in the opinion of the treating physician or physician performing the biopsy that the biopsy will pose significant risk to the patient, or 3) if the biopsy sample obtained on the first attempt is not adequate.*
- A complete medical history will be obtained from each patient. Medical history will include baseline symptoms of the disease under study as well as a detailed history of prior procedures for the patient's NHL or advanced solid malignancy and other prior cancer therapies (i.e., chemotherapy, hormonal therapy, immunotherapy, biotherapy, radiotherapy, and surgery), including start and end dates, best response, disease progression during or after therapy, as well as discontinuations due to intolerance, toxicity, or any other serious illness; Tumor Nodes Metastasis (TNM) staging will be collected on for patients with advanced solid malignancies. Smoking history will be recorded. A detailed history of disease-specific diagnostic and prognostic testing and test results (such as phenotypic and cytogenetic profiles) will also be collected.
- Vital signs: blood pressure, pulse and body temperature; see Section 7.5.1.2 for a detailed description of vital sign assessments.

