- 16 Safety follow-up telephone call [30 days post-last dose (+ 7 days)] with patient after their last dose of study treatment to evaluate their overall medical condition and status of disease, AEs, including follow-up on any AEs that were not resolved at the EoT Visit, and collection of information on any antineoplastic therapies used after discontinuation of study treatment.
- 17 At the Investigator's discretion, in consultation with the Karyopharm Medical Monitor, patients with clinically significant hematological AEs, including any grade of treatment-emergent anemia or abnormal reticulocyte counts, may have a hematology consultation. Hematological testing (including but not limited to standard hematological evaluations and erythropoietin level) \pm bone marrow biopsy may be performed as clinically indicated per institutional standards.

18 Patients with treatment-emergent anemia should have blood levels of vitamin B12, folate, iron, erythropoietin, haptoglobin, and transferrin and reticulocyte counts assessed as soon as possible after onset. Patients with \leq Grade 1 anemia should have their levels/counts assessed no less than once a month and patients with \geq Grade 2 anemia should have their levels/counts assessed every 2 weeks.

19 For explorative analysis research procedure, tumor tissue will be obtained pre- treatment (Day -30 to Day 1) , C3D1 (\pm 7 days), and at the time of progression. Each biopsy will be divided into 3 portions, resulting in two fresh biopsies and one formalin fixed biopsy. *For the biopsies on C3D1 and EoT, patients will be allowed to continue treatment if: 1) a patient refuses the biopsy, 2) in the opinion of the treating physician or physician performing the biopsy that the biopsy will pose significant risk to the patient, or 3) if the biopsy sample obtained on the first attempt is not adequate.*

20 Advanced solid malignancies: CT, MRI, or PET-CT scans will be performed at screening (Day -30 to Day -1), then every 8 weeks \pm 7 days (e.g., Day 1 of odd numbered cycles), until disease progression or the EoT visit and Durability of Response and Survival Follow-up. EoT scan is only required for patients who end treatment for reasons other than disease progression. The same scan modality should be used for all assessments. Durability of Response and Survival Follow-up scan is only for patients who have not progressed.

[figure not shown]

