11. Dose Escalation Phase: Patients will be enrolled according to their NAPRT1 status at a ratio of 2:1 (NAPRT1 negative:NAPRT1 positive). The NAPRT1 status must be determined prior to enrollment based on evaluation of a fresh tumor biopsy or archival tissue taken ≤ 6 months of screening.
12. Dose Expansion Phase (KPT-9274 \pm niacin ER cohort only): Patient tumors NAPRT1 and IDH1 status must be determined at the central laboratory prior to enrollment.
 - a. Confirmation of NAPRT1 expression and IDH1 mutation based on evaluation of a fresh tumor biopsy or archival tumor biopsy taken ≤ 6 months of screening tests as follows:
 - i. NAPRT1 positive for expansion cohort I or III
 - ii NAPRT1 negative for expansion cohort II or III
 - iii. IDH1 mutation status for expansion cohort IV
13. Life expectancy of ≥ 3 months.

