6.2.3. Dosing Information

Patients will receive oral KPT-9274 three times a week every other day (Days 1, 3, 5, 8, 10, 12, 15, 17, 19, 22, 24, and 26) during each 28-day cycle.

Study treatment will be administered in the clinic and at home as indicated in [Table 4](#). Study treatment dosing will occur in the clinic during Cycle 1 on Days 1, 3, 8, 15, 22, 24, and 26, during Cycle 2 on Days 1, 8, 15, and 22, and during \geq Cycle 3 on Days 1 and 15. Study treatment dosing will occur at home during Cycle 1 on Days 5, 10, 12, 17, and 19, during Cycle 2 on Days 3, 5, 10, 12, 17, 19, 24, and 26 and during Cycles \geq 3 on Days 3, 5, 8, 10, 12, 17, 19, 22, 24, and 26.

During Part B of the Dose Escalation Phase, patients will receive 500 mg niacin ER co-administered with each dose of KPT-9274. The starting dose of 500 mg niacin ER may be titrated to 2,000 mg of daily dose, per label. The starting dose for KPT-9274 in Part B will be a dose and schedule that cleared DLT assessment during Part A. For the purposes of dose escalation decisions, a standard 3+3 dose escalation design will be used during both Part A and Part B.

A total of ~65 patients with advanced solid malignancies and NHL may be enrolled to further explore safety, tolerability and preliminary evidence of anti-tumor activity of the RP2D of KPT-9274 \pm niacin ER. After declaring the RP2D \pm niacin ER (see Section [6.2.6](#)), based on the safety and tolerability results of the Dose Escalation Phase, a decision will be made whether expansion (4 groups, ~45 patients total) will be conducted at the RP2D of KPT-9274 single agent or at the RP2D of KPT-9274 + niacin ER. If the 45 patient expansion is conducted at the RP2D of KPT-9274 + niacin ER, an optional expansion with < 20 patients at the RP2D of KPT-9274 single agent may be initiated. Futility analyses based on clinical efficacy will be conducted in a maximum of 10 patients dosed at the RP2D \pm niacin ER (see Section [6.2.7](#) for additional details).

Dose escalation will occur according to the Dose Escalation Guidelines provided in Section [6.2.6](#).

Patients with melanoma enrolled in Part C, KPT-9274 + nivolumab, cohort will receive nivolumab (480 mg once per 28 day cycle) according to the current prescribing information.

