Patients must complete a minimum of 1 cycle of treatment, defined as receiving \geq 75% of KPT-9274 doses during Cycle 1 (e.g., \geq 9 of 12 doses in the 3 doses/week schedule), or have a DLT within the first cycle of treatment to be evaluable for dose escalation decisions. Dose escalation decisions will occur when the cohort of patients has met these criteria.

Dose escalation decisions will be made by enrolling Investigators and Karyopharm study personnel. Decisions will be based on an evaluation of all relevant data available from all dose levels evaluated in the ongoing study including safety information, DLTs, all CTCAE (Version 4.03) toxicity data during Cycle 1 and PK data (if available) from evaluable patients (see Section [6.2.6.3](#))

[Table 13](#) describes the starting dose and the dose cohorts that may be evaluated in Part A. A similar dose escalation plan will be used in Part B. To better evaluate the safety, tolerability and PK of KPT-9274, additional cohorts of patients may be enrolled on alternate dosing schedules, at preceding dose levels, or to intermediate dose levels before or while proceeding with further dose escalation.

Dose escalation for Part A and Part B will be conducted as follows:

- If 0 of 3 patients experiences a DLT, escalate to next higher dose cohort.
- If 1 of 3 patients experiences a DLT, that cohort will be expanded to 6 patients. If 1 of 6 patients experiences a DLT, escalate to the next higher dose cohort;
- If \geq 2 of 3 or \geq 2 of 6 patients experience a DLT, MTD is exceeded. If the MTD is exceeded, the patients will be de-escalated to the next lower dose level (the MTD).

Part C (KPT-9274 + nivolumab):

The initial cohort will consist of 3 enrolled patients who will be treated at a dose of 30 mg KPT-9274, co-administered with a dose of 480 mg nivolumab. If these patients do not experience a DLT during Cycle 1, the KPT-9274 dose will be escalated to 40 mg for another cohort of 3 patients upon approval during a dose decision meeting. A maximum of 10 patients may be enrolled at each dose level.

Additional KPT-9274 dose levels (e.g., 20 mg or 60 mg) may be evaluated if an optimal dose is not identified and the safety review committee is in agreement.

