7.2.5. Determination of NAPRT1 and IDH1 Tumor Status

NAPRT1 and IDH1 tumor status for Parts A and B must be determined prior to enrollment in the KPT-9274 ± niacin ER escalation and expansion cohorts. Archival biopsy material obtained \leq 6 months prior to screening may be used to prescreen patients for NAPRT1 and IDH1 tumor status. A fresh biopsy will be collected during screening to determine or confirm that NAPRT1 and IDH1 tumor status. Screening period includes Day -30 to Day 7 prior to C1D1. Additional details are provided in Section 7.4.3.3.

7.2.6. Determination of Patients with Melanoma Who Progressed on Prior Anti-PD-1 or Anti-PD-L1 Treatment

Patients with melanoma who progressed on prior anti-PD-1 or anti-PD-L1 treatment must be determined prior to enrollment in Part C - KPT-9274 + nivolumab. Screening period includes Day -30 to Day -1 prior to C1D1.

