Starting from Cycle 1 Day 1 (C1D1), blood will be drawn at 0 h (< 15 mins prior to dosing), 3 h \pm 15 mins, 6 h \pm 30 mins, 8 h \pm 30 mins, 24 h \pm 60 mins, and 48 h \pm 60 mins. Cycle 2 Day 1 (C2D1), blood will be drawn at 0 h (< 15mins prior dosing), 3 h \pm 15 mins, , 6 h \pm 30 mins, 8 h \pm 30 mins, 24 h \pm 60 mins, and 48 h \pm 60 mins after C2D1 dose. Time since last meal and a description of the meal contents will be reported by the patient to the treating physician prior to each PK blood draw. PK assessments are outlined in [Table 18](#).

CCI

CCI

[figure not shown]

Table 17: Collection Time Points and Sample Volumes for PK and CCI for Parts A and B

Time Point	Total Volume of Blood (mL)	Number of Tubes by Volume of Blood		Biopsy
		PK	CCI	
		1 tube x 2.0 mL		
Screening				
Between D -30 and D 7	--	--		2 fresh biopsies and 1 formalin fixed biopsy
C1D1 (repeat if patient dose changes)				
Pre-dose (< 10 min before KPT-9274 dosing)	13	X		--
0.5 hr (\pm 5 min) post-dose	2	X		--
1 hr (\pm 10 min) post-dose	2	X		--
2 hr (\pm 10 min) post-dose	2	X		--
4 hr (\pm 20 min) post-dose	13	X		--
8 hr (\pm 30 min) post-dose	13	X		--
C1D2 (repeat if patient dose changes)				
24 hr (\pm 2 hours) after intake of first dose on C1D1	13	X		--
C1D3 (repeat if patient dose changes)				
48 hr (\pm 2 hours) after intake of first dose on C1D1, prior to C1D3 dose	13	X		--
C1D8				
Pre-dose (< 10 min before KPT-9274 dosing)	13	X		--
2 hr (\pm 10 min) post-dose	2	X		--
C1D15				

Time Point	Total Volume of Blood (mL)	Number of Tubes by Volume of Blood		Biopsy
		PK	CCI	
Pre-dose (< 10 min before KPT-9274 dosing)	13	X		--
2 hr (\pm 10 min) post-dose	2	X		--

Time Point	Total Volume of Blood (mL)	Number of Tubes by Volume of Blood		Biopsy
		PK	CCI	
		1 tube x 2.0 mL		Lymph Node Biopsy and/or Tumor Biopsy
C1D24				--
Pre-dose (< 10 min before KPT-9274 dosing)	13	X		--
2 hr (\pm 10 min) post-dose	2	X		--
4 hr (\pm 20 min) post-dose (Expansion Phase only) ²	2	X		--
8 hr (\pm 30 min) post-dose	13	X		--
12 hr (\pm 60 min) post-dose (Expansion Phase only) ²	2	X		--
18 hr (\pm 60 min) post-dose (Expansion Phase only) ²	2	X		--
C1D25				--
24 hr (\pm 2 hours) after intake of dose on C1D24	13	X		--
32 hr (\pm 2 hours) after intake of dose on C1D24 (Expansion Phase only) ²	2	X		--
C1D26				2 fresh biopsies and 1 formalin fixed biopsy ¹
48 hr (\pm 2 hours) after intake of dose on C1D24, prior to C1D26 dose	13	X		--
1 hr (\pm 10 min) post-dose	2	X		--

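### In Parts A and B the screening biopsy window runs to Day 7, after up to three doses, and contradicts the rest of the protocol; exploratory baseline tissue could be on-treatment

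*Protocol*

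**What the plan says.** Three current places in the protocol give Day 7 as the last day of the Parts A and B window:

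- Section 7.2.5, on NAPRT1 and IDH1 status: "Screening period includes Day -30 to Day 7 prior to C1D1".
- Footnote 2 to Tables 1 to 3, on tumor tissue for exploratory research: "will be obtained pre- treatment (Day -30 to Day 7), C1D26".
- Table 17, screening row for two fresh biopsies and one formalin-fixed biopsy: "Between D -30 and D 7".

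Other current text points to a window that closes before treatment:

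- Table 1 marks marker determination and the pre-treatment biopsy in the Day -30 to Day -1 screening column. The next biopsy mark is at Day 26 (±7 days).
- Section 3.1 places screening before the start of therapy, and Section 4.6 ends it on C1D1.
- Inclusion criterion 11 (Section 4.2) says "The NAPRT1 status must be determined prior to enrollment". Criterion 12 and Section 7.2.5 also require status before enrollment.

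For Part C, the Table 18 screening row ends at Day -1, whereas footnote 19 to Tables 5 to 7 reads "tumor tissue will be obtained pre- treatment (Day -30 to Day 1".

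Dosing under Section 6.2.3 falls on "Days 1, 3, 5, 8, 10, 12, 15, 17, 19, 22, 24, and 26) during each 28-day cycle".

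**The concern.** A sample taken on Days 2 to 7 follows at least one dose and is not pre-treatment, whatever its label. Section 7.2.5 contradicts itself within one sentence, since Day 7 is not before C1D1. Footnote 2 and Table 17 set no limit of their own other than Day 7, so a site working from either could take the baseline biopsy a week into treatment and believe it had complied.

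What is at stake is mainly the baseline for exploratory tissue work. Section 1.3.3 says the drug lowers the steady-state level of PAK4. Appendix 6, explaining inclusion criterion 5, says biopsies are wanted partly to show target engagement by measuring PAK4, NAMPT or downstream signaling. Tissue taken after several doses may already carry part of the effect that it is meant to be compared against.

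The secondary stake is marker status. The fresh screening biopsy is meant to determine or confirm NAPRT1 and IDH1 status. NAPRT1 status governs the 2:1 escalation enrollment, and both markers define the expansion groups.

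**Working it through.** **Inputs.** Dosing days are from Section 6.2.3. The number of doses per cycle is from Section 6.2.6.1 ("9 of 12 doses in the 3 doses/week schedule"). The window ends are from Section 7.2.5, footnote 2, Table 17, Table 18 and footnote 19. The second biopsy is at C1D26 ±7 days (footnote 2).

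**The plan's own figure.** Counting Days 1, 3, 5, 8, 10, 12, 15, 17, 19, 22, 24 and 26 gives 12 doses, and 9/12 = 75%. This agrees with the evaluability rule in Section 6.2.6.1.

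**Doses that can precede the baseline biopsy, by end of window:**

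| Window ends | Source | Doses possible before biopsy | Share of Cycle 1 |
|---|---|---|---|
| Day -1 | Table 1; Part C Table 18 | 0 | 0/12 = 0% |
| Day 1 | Part C footnote 19 | 0 if pre-dose, 1 if not | at most 1/12 = 8.3% |
| Day 7 | Section 7.2.5, footnote 2, Table 17 | 3 (Days 1, 3, 5) | 3/12 = 25% |

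**Spacing of the pair in the worst case.** The second biopsy may be taken from Day 26 - 7 = Day 19 to Day 26 + 7 = Day 33. The shortest interval from a Day 7 sample is 19 - 7 = 12 days. By Day 19 a patient has had 8 doses, or 9 if that day's dose comes first. The two samples would then be separated by 8 - 3 = 5 or 9 - 3 = 6 doses. With a true pre-dose baseline they would be separated by 8 or 9.

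**A lost minus sign?** Loss in reading the PDF is unlikely. Day 7 appears in three separate places, each time beside a -30 that kept its sign, and Section 7.2.6 and Table 18 print Day -1 correctly. The Appendix 6 entry for Version 4.1 also records Day -30 to Day 7 as a deliberate clarification of footnote 2. An authoring slip for a negative day remains possible, and the documents cannot settle it.

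**The case against.** The strongest reply is that the plan already blocks most of the harm.

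**Marker status.** A reader might infer that 2:1 enrollment and the expansion groups could rest on post-dose tissue. The documents do not support that. Criteria 11 and 12, footnote 2 and Section 7.2.5 all require status before enrollment. Criteria 11 and 12 accept archival tissue up to 6 months old, and Section 4.6 has eligibility reviewed before the first dose. If these rules are followed, at most a confirmatory sample would be late. This objection stands.

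**Baseline tissue.** A reader might also infer that the baseline is contaminated and that change to C1D26 is therefore hidden. That goes too far. Footnote 2 labels the tissue exploratory, and the exploratory objectives are redacted. Section 7.4.3.3, to which Section 7.2.5 refers, is not in the text available here. SAP Sections 1.2.3 and 2 leave some analyses to separate plans. Whether a paired analysis is planned, and how post-dose tissue would be handled in it, cannot be seen. The documents do not show how quickly these markers move under treatment or how many biopsies fell on Days 2 to 7. Blunting is a risk, not an established effect.

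**Importance.** The primary and secondary endpoints set out in the plan do not use this biopsy, and SAP Section 2.8 plans no subgroup analysis. SAP Section 2.6 defines baseline as the last value before first dose, which would exclude Day 2 to 7 tissue if it governs this work. These points limit the consequences.

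The wording itself remains. Footnote 2 and Table 17 permit what Table 1 and Section 4.6 do not.

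**Conclusion.** The point holds as an internal contradiction in the schedule, in which one reading permits on-treatment tissue to be collected as baseline. It is not a consistent instruction to collect such tissue. The size is up to 3 of 12 Cycle 1 doses (25%) before the baseline sample. The 12-day spacing is an extreme that pairs the latest first biopsy with the earliest second one.

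The figures assume the three-doses-a-week schedule with no missed doses. The two-days-a-week option in Section 6.2.5 would give fewer doses by Day 7. The practical effect depends on how many patients were biopsied on Days 2 to 7, which is unknown.

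The contradiction should be corrected. It affects the interpretability of exploratory tissue results and, to a lesser degree, the timing of marker confirmation. It does not affect the dose-finding or efficacy endpoints.

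**What to change.** 1. Reconcile Section 7.2.5, footnote 2 to Tables 1 to 3 and the Table 17 screening row with Table 1, so that the Parts A and B window closes before the first dose. Day -1, as in Part C Table 18, is the clean model.
2. Align Part C footnote 19 by changing Day 1 to Day -1 or by adding that the sample is pre-dose. It should not serve as the model as it stands. Day 1 is a dosing day, and pre-dose sampling follows only from the general note that clinic procedures precede dosing.
3. In whichever plan governs the tissue analyses, state that any sample taken after the first dose is on-treatment and is left out of baseline comparisons, in line with SAP Section 2.6. Record biopsy date and time relative to the first dose so that the rule can be applied to samples already collected.

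The cost is a few words in four places and one analysis rule. Sites lose some scheduling room before C1D1, and a few samples may drop out of paired analyses.

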7.3. Efficacy Assessments

7.3.1. Non-Hodgkin's Lymphoma and Advanced Solid Malignancy Assessments

7.3.1.1. Quality of Life

QoL will be assessed using the European Organization for Research and Treatment of Cancer (EORTC) QLQ-C30 Questionnaire for all patients and the Functional Assessment of Cancer Therapy and Lymphoma (FACT-Lym) Questionnaire ([Webster, 2005](#)) for patients with NHL.

The QoL assessments will be performed at Screening before undergoing any study procedures (including discussions with medical personnel and administration of study treatment) on Day 1 of each cycle and at the EoT Visit.

The EORTC QLQ-C30 is a validated, patient self-administered instrument for assessing the health-related QoL of cancer patients participating in international clinical trials. It is a questionnaire containing both multi-item and single scales, including five functional scales (physical, role, emotional, social and cognitive), three symptom scales (fatigue, nausea & vomiting and pain) and a global health status/QoL scale and six single items (dyspnea, insomnia, appetite loss, constipation, diarrhea, and financial difficulties).

NHL patients only: The FACT-Lym combines the General version of the Functional Assessment of Cancer Therapy (FACT-G) with a lymphoma-specific subscale (15 items). The subscales for the FACT-G are Physical Well-Being (7 items), Social/Family Well-Being (7 items), Emotional Well-Being (6 items), and Functional Well-Being (7 items). The trial outcomes index (TOI; total of 29 items) will be the primary measurement of interest, comprised of the Physical and Functional subscales plus the lymphoma-specific subscale. Each item is rated on a 5-point Likert scale, ranging from 0 ("Not at all") to 4 ("Very much"), therefore the TOI has a score ranging from 0 to 116.

7.3.2. Non-Hodgkin's Lymphoma Only Assessments

Patient response will be assessed by the procedures described in the following subsections and graded according to the Lugano Classification (NHL) summarized in [Appendix 3](#).

7.3.2.1. PET-CT (or CT) Scan

Disease response will be preferably based on tumor measurement using PET/CT for FDG-avid lymphomas, or CT for non-FDG-avid lymphomas (or PET/MRI or MRI if CT is contraindicated) scans. Scans will be conducted at Screening (Day -30 to Day -1) and after every 8 weeks ±

7 days (e.g., Day 1 of odd numbered cycles) until disease progression or the EoT visit. EoT scan is only required for patients who end treatment for reasons other than disease progression. The same scan modality should be used for all assessments. PET/CT for FDG-avid lymphomas or CT for non-FDG-avid lymphomas (or PET/MRI or MRI if CT is contraindicated) is strongly preferred.

7.3.2.2. Bone Marrow Aspirate and/or Biopsy

Bone marrow biopsies and/or aspirates will be taken within 30 days prior to first dose (baseline) to assess NHL involvement in bone marrow. The bone marrow biopsy will be repeated whenever clinically indicated, at the discretion of the Investigator, to confirm CR/PR only in those patients who had NHL with known bone marrow involvement prior to dosing.

